2.3 Study endpoints

Main endpoints and definitions:

This study primarily evaluates the proportion of patients with YWHAB

high expression locally advanced rectal cancer who achieve tumor downstaging (ypTNM 0-I stage) after neoadjuvant therapy with mFOLFOX6 combined with Citrus Flavonoid Tablets (Aimianlang). The tumor downstaging rate (ypTNM 0-I stage) refers to the percentage of patients with locally advanced rectal cancer who, after receiving neoadjuvant chemotherapy with mFOLFOX6 or mFOLFOX6 + Citrus Flavonoid Tablets (Aimianlang), have their postoperative pathological stage of the surgical specimen classified as ypTNM 0-I stage.

Secondary endpoints and definitions:

- (1) The degree of pathological remission is defined as follows: ① Complete Remission (CR): All tumor target lesions have disappeared, no new lesions have appeared, and tumor markers are normal, lasting at least 4 weeks. ② Partial Response (PR): The sum of the maximum diameters of tumor target lesions has decreased by at least 30%, lasting at least 4 weeks. ③ Stable Disease (SD): The sum of the maximum diameters of tumor target lesions has not decreased by more than PR, or increased by less than PD. ④ Disease Progression (PD): The sum of the maximum diameters of tumor target lesions has increased by at least 20%, or new lesions have appeared.
- (2) The 3-year disease-free survival rate (DFS) is the proportion of patients who have not experienced any of the following events from the start of randomization to the end of year 3: disease progression, surgical gross/microscopic tumor residue, local recurrence, distant metastasis, or death for any reason, whichever occurs first.
- (3) Overall survival time (OS) is the time from randomization to death for any reason.
- (4) Tumor regression grading TRG: TRG 0 means no residual tumor cells, TRG 1 means a single cell or a small group of cells; TRG 2 means residual cancer with a proliferative response to connective tissue; TRG 3 means minimal evidence of tumor response.
- (5) Safety indicators, treatment-related adverse reaction rate (grade III and

above): Antitumor drugs/therapy In clinical trials, drug adverse reactions determined to be related to drug therapy at grade III and above, excluding nonspecific infusion reactions.

3. Selection and withdrawal of subjects

3.1 Inclusion criteria:

- (1) Histopathology was diagnosed as rectal adenocarcinoma, all other histological types were excluded, and the colonoscopy report or clinical physical examination suggested the presence of hemorrhoids;
- (2) The clinical pathological stage of the tumor is T3-4 or N+ and M0; 8th edition AJCC TNM staging, Appendix 1)
- (3) Immunohistochemical staining of tissue samples showed that YWHAB was highly expressed in rectal cancer patients;
- (4) The age of obtaining informed consent is 18-75 years old;
- (5) Eastern United States Cooperative Group Physical Status Score (ECOG) was 0-1 points (refer to Appendix 3);
- (6) No previous systemic anti-tumor treatment for rectal cancer, including cytotoxic drugs, immune checkpoint inhibitors, molecular targeted therapy, endocrine therapy, etc.;
- (7) Based on the following laboratory test values obtained during the screening period, appropriate organ function is present: white blood cell count $\geq 3 \times 10^9/L$, neutrophil count $\geq 1.5 \times 10^9/L$, platelet count $\geq 75 \times 10^9/L$, serum total bilirubin $\leq 1.5 \times$ upper limit of normal (UNL), aspartate aminotransferase or alanine aminotransferase $\leq 2.5 \times$ UNL, serum creatinine $\leq 1.5 \times$ UNL;
- (8) Women of childbearing age must have a negative serum pregnancy test within 3 days prior to the start of study medication and be willing to use a medically recognized effective contraceptive method (e.g., IUD, pill, or condom) during the study and for 3 months after the last dose of study medication;

- (9) For male subjects whose partner is a woman of reproductive age, effective contraception was used during the study and for 3 months after the last study dose;
- (10) The subject has given his/her own consent and signed an informed consent form, and the subject is willing and able to comply with the planned visits, research treatment, laboratory tests and other trial procedures.

3.2 Exclusion criteria:

- (1) Whole body CT, MR or PET-CT (at least including chest, whole abdomen and pelvis) confirmed distant metastasis;
- (2) Whole genome testing for DPD enzyme deficiency or 7/7 homozygotes for UGT1A1*28 locus in patients;
- (3) The patient has complete intestinal obstruction, active bleeding or perforation and requires emergency surgery;
- (4) Previous or concurrent presence of other active malignancies (excluding malignancies that have been treated curatively and have not recurred for more than 5 years or carcinoma in situ that can be cured by adequate treatment);
- (5) Having had a thrombotic or embolic event, such as a cerebrovascular accident (including transient ischemic attack), pulmonary embolism, or deep vein thrombosis, within 12 months prior to enrollment;
- (6) In the 12 months prior to enrollment, the following conditions occurred: myocardial infarction, severe/unstable angina, NYHA class II or higher heart failure, clinically significant supraventricular or ventricular arrhythmias, and symptomatic congestive heart failure;
- (7) Systemic use of antibiotics for more than 7 days within 4 weeks prior to enrollment, or unexplained fever >38.5°C during screening/ prior to first dose (fever due to tumor can be enrolled by investigator);
- (8) Received major surgery or severe trauma, such as cesarean section, thoracotomy, or organ resection through laparoscopic surgery, within 2

months prior to enrollment (surgical incisions should be completely healed before enrollment in this clinical trial);

- (9) Known to have human immunodeficiency virus (HIV) infection or acquired immunodeficiency syndrome (AIDS)-related diseases;
- (10) The presence of interstitial lung disease, non-infectious pneumonia or uncontrolled systemic diseases (e.g., diabetes, hypertension, pulmonary fibrosis and acute pneumonia);
- (11) Untreated active hepatitis (Hepatitis B, defined as HBV-DNA \geq 500 IU/mL; Hepatitis C, defined as HCV-RNA above the detection limit of the assay) or co-infection with hepatitis B and C;
- (12) A known or suspected history of allergy to any relevant drug used in the study;
- (13) Patients who the researchers thought were not suitable for the study.

3.3 Exit criteria:

Participants may withdraw from the trial at any time, or be asked to withdraw by the investigator or sponsor for safety or behavioral reasons or because they are unable to comply with the study visit time or steps required by the protocol. Withdrawal criteria include:

- (1) The subject withdrew the informed consent to participate in the study and refused further follow-up;
- (2) Clinical adverse events, laboratory abnormalities or concurrent diseases occur and the subject considers it not in the best interest of the subject to continue to participate in the study;
- (3) A general deterioration of health status, making it impossible to continue participation in the trial;
- (4) Pregnancy events in subjects during the study;
- (5) Significant deviations from the protocol, such as unqualified or non-compliance of subjects, were found after enrollment;
- (6) Disappearance;

- (7) Subject death;
- (8) The researchers identified other situations in which withdrawal from the study was necessary, such as significant protocol violations.

4. Research treatment

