2.1 Overall design of the study

This study is a prospective, open, double-arm, phase II clinical trial to explore the mFOLFOX6 combined with citrus flavonoid tablets (Aimalang) regimen as neoadjuvant therapy for YWHAB high expression locally advanced rectal cancer. The study design is in accordance with ethical requirements.

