4.1 Study treatment grouping

This study is a prospective, open-label, double-arm, Phase II clinical trial that includes a neoadjuvant treatment group using the mFOLFOX6 regimen and a neoadjuvant treatment group combining the mFOLFOX6 regimen with Citrus Flavonoid Tablets (Aimalang). The study aims to enroll patients with locally advanced rectal cancer who are in clinical stage I, II, or III. Endoscopic biopsy specimens will be collected for YWHAB immunohistochemical testing to identify patients with high YWHAB expression in locally advanced rectal cancer. These patients will then be randomly assigned to either the mFOLFOX6 treatment group or the mFOLFOX6 combined with Citrus Flavonoid Tablets (Aimalang) treatment group for neoadjuvant therapy. The mFOLFOX6 regimen involves 4-6 cycles before surgery and 6-8 cycles after surgery, with each cycle lasting 14 days: on day 1, 85 mg/m² of oxaliplatin is administered intravenously over 180 minutes; on day 1, 400 mg/m² of leucovorin is administered intravenously over 120 minutes; and on day 1, 2400 mg/m² of 5-fluorouracil is administered continuously intravenously for 46 hours. The Citrus Flavonoid Tablets (Aimalang) treatment regimen involves taking 500mg of Citrus Flavonoid Tablets (Aimalang) orally three times daily, with doses given on days 1-14 of each 14-day cycle.

This trial allows for dose adjustments. Patients who experience disease progression during neoadjuvant therapy may stop the study treatment and directly undergo surgery or follow local guidelines. If a patient cannot tolerate the planned 6 cycles of neoadjuvant therapy, early surgery can be considered. Any patient who has received another anticancer regimen before surgery will stop the study treatment and be managed according to local guidelines. The postoperative

treatment for both groups is determined by the investigator, which may include continuing the mFOLFOX6 regimen combined with Citrus Flavonoid Tablets (Aimalang). It is important to note that all patients in the control group are prohibited from taking Citrus Flavonoid Tablets (Aimalang) without authorization during the trial. If a patient needs to take this medication for any reason, they should consult their primary physician, who will decide whether to use an alternative or discontinue the patient's participation in the trial.

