The main efficacy indicator of this study was the proportion of patients in each treatment group who achieved tumor downstaging (ypTNM 0-I stage), and the secondary efficacy indicators were the proportion of patients with complete pathological remission, 3-year disease-free survival (DFS), overall survival time (OS) and tumor regression grade TRG.

6.2 Evaluation criteria of effectiveness:

This study evaluated the proportion of patients with YWHAB high expression locally advanced rectal cancer who achieved tumor downstaging (ypTNM 0-I stage) in neoadjuvant treatment with mFOLFOX6 combined with citrus flavonoid tablets (Aimalang).

- (1) Downstaging rate of tumor (ypTNM 0-I stage): the proportion of patients with locally advanced rectal cancer who received mFOLFOX6 or mFOLFOX6 combined with citrus flavonoid tablets (Aimalang) as neoadjuvant chemotherapy, and the proportion of patients with postoperative pathological stage of ypTNM 0-I stage in surgical specimens.
- (2) The degree of pathological remission is defined as follows: ① Complete Remission (CR): All tumor target lesions have disappeared, no new lesions have appeared, and tumor markers are normal, lasting at least 4 weeks. ② Partial Response (PR): The sum of the maximum diameters of tumor target lesions has decreased by at least 30%, lasting at least 4 weeks. ③ Stable Disease (SD): The sum of the maximum diameters of tumor target lesions has not decreased by more than PR, or increased by less than PD. ④ Disease Progression (PD): The sum of the maximum diameters of tumor target lesions has increased by at least 20%, or new lesions have appeared.

Subjects who did not meet the primary endpoint criteria are included in the denominator but not in the numerator.

- (3) When determining the disease-free survival (DFS), clinical deterioration without clear evidence of disease progression according to the RECIST 1.1 criteria is not considered a disease progression. For subjects who died without prior reported disease progression, it is considered that the disease progressed at the time of death. Subjects who have neither experienced disease progression nor died will be censored at their last evaluable tumor evaluation date. Independent central imaging review will be conducted to confirm the independent central imaging service provider of the subject, which will receive all images from the research center and assess the subject's disease progression according to the RECIST 1.1 criteria.

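### No masking is specified for the reader of the surgical specimen, which decides the primary endpoint (ypTNM 0-I) and TRG in this open-label trial

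*Combined protocol and SAP*

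**What the plan says.** Section 2.1 describes the design: "This study is a prospective, open, double-arm, phase II clinical trial". Section 4.1 has eligible patients "randomly assigned to either the mFOLFOX6 treatment group or the mFOLFOX6 combined with Citrus Flavonoid Tablets" and gives no allocation ratio. Both arms receive mFOLFOX6; the experimental arm adds an oral tablet.

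Section 2.3 defines the primary endpoint by patients who "have their postoperative pathological stage of the surgical specimen classified as ypTNM 0-I stage". Section 6.2 repeats it as "the proportion of patients with postoperative pathological stage of ypTNM 0-I stage in surgical specimens". Section 2.3 also defines TRG from residual tumour: "TRG 0 means no residual tumor cells, TRG 1 means a single cell or a small group of cells".

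No section names the specimen reader, says whether that person knows the arm, plans a second or central pathology read, or describes how specimens are sampled.

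For DFS, section 6.2 does plan an outside assessment: "Independent central imaging review will be conducted". The provider is one "which will receive all images from the research center and assess" progression by RECIST 1.1. The plan describes no other independent assessment of an endpoint.

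**The concern.** ypTNM 0-I is a single yes/no cut on a pathology reading. Which side a patient falls on can depend on how thoroughly the tumour bed is sampled, how many nodes are retrieved, and how a borderline ypT2/ypT3 case is called. TRG 0 against TRG 1 turns on whether a few residual cells are found, so it has the same exposure.

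Reading error that is the same in both arms does not create a difference when the true rates are equal. Error that depends on knowing the arm does, and an open-label trial leaves that route open unless the plan closes it. The plan arranges independent assessment for part of a secondary endpoint but states no comparable safeguard for the reading that decides the trial. What is at stake is the credibility of the primary comparison.

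**Working it through.** **The texts side by side**

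| Endpoint | Role | Source of the reading | Safeguard stated |
|---|---|---|---|
| ypTNM 0-I | Primary | Surgical specimen (2.3, 6.2) | None |
| TRG | Secondary | Residual tumour cells (2.3, 6.2) | None |
| DFS, imaging progression | Secondary | Imaging, RECIST 1.1 (6.2) | Independent central review; blinding not mentioned |
| DFS, residual tumour at surgery | Secondary | Surgery and pathology (2.3) | None |

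The gap is established by reading alone. The arithmetic below shows only how sensitive the primary comparison would be.

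**Inputs**

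- Total sample size 236 (section 8.5). The ratio is not stated; 1:1 is assumed, so 236 / 2 = 118 per arm.
- Control downstaging rate 25% (section 8.5).
- Significance level 0.05, sidedness not stated (section 8.5). Both versions are shown.
- Test: section 8.3 names no between-group test for downstaging. A pooled two-proportion z-test is assumed.
- Size of the reading shift: an assumption. Shifts of 1, 3 and 5 points are shown.

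**The plan's figure.** The unpooled one-sided formula with 25% against 40% and 80% power gives (1.645 + 0.842)² × (0.25×0.75 + 0.40×0.60) / 0.15² = 117.5, so 118 per arm and 236 in total. That is before the stated 10% dropout, which would make it 264. The mismatch is a separate matter; 236 serves here only as the planned size.

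**Method.** Let both true rates be 25%, and let the experimental arm be read at 25% + s. Count a false positive when

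z = (p̂E − p̂C) / √[p̄(1 − p̄) × 2/118]

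is at least 1.645 (one-sided 0.05) or at least 1.960 (favourable tail of a two-sided 0.05 test). The binomial probabilities of all outcome pairs that meet the criterion are summed exactly.

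| Shift s | Patients (118 × s) | One-sided | Two-sided, favourable tail |
|---|---|---|---|
| 0 | 0 | 5.0% | 2.5% |
| 1 point | 1.2 | 7.1% | 3.7% |
| 3 points | 3.5 | 13.1% | 7.5% |
| 5 points | 5.9 | 21.6% | 13.6% |

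**Hand check at 3 points.** p̄ = 0.265. The null standard error is √(0.265 × 0.735 × 2/118) = 0.0575. The alternative is √[(0.25×0.75 + 0.28×0.72)/118] = 0.0574. One-sided: Φ[(0.03 − 1.645 × 0.0575)/0.0574] = Φ(−1.12) = 13.1%. The favourable two-sided tail is Φ(−1.44) = 7.5%.

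**A second model.** Suppose instead that a share m of experimental patients who are not downstaged is read as ypTNM 0-I, so the apparent rate is 0.25 + 0.75m. By normal approximation with 118 per arm, m = 2%, 5% and 10% gives apparent rates of 26.5%, 28.75% and 32.5%. The one-sided rates are 8.4%, 16.0% and 35.5%, and the favourable two-sided tails 4.5%, 9.5% and 24.5%. With 106 per arm (118 less 10%), the one-sided rates are 8.2%, 15.2% and 33.0%. The pattern does not depend on the model.

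**The case against.** The strongest reply is that silence is not evidence of an unmasked read. Several stronger readings are tempting, and the documents do not support them.

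- *That the pathologist is unmasked, or that readers are local.* No section says either. The arms share mFOLFOX6 and differ in an oral tablet, and no section says that allocation reaches pathology. What stands is that masking is not specified, so an arm-aware read would be within protocol.
- *That pathological remission is exposed in the same way.* Despite its name, sections 2.3 and 6.2 define it by target-lesion diameters, new lesions, tumour markers and a four-week duration. As written it is not a specimen reading. The point covers ypTNM and TRG only.
- *That DFS has a blinded safeguard which the primary endpoint was denied.* The review is called independent, never blinded, and its sentence is garbled: "Independent central imaging review will be conducted to confirm the independent central imaging service provider". It covers progression on imaging, not residual tumour at surgery or death. The contrast is real but limited, and masking a pathologist is a different safeguard from central review.
- *That the trial's type I error will be 13% or 22%.* Those figures need every net misreading to favour one arm. They also assume a shift that the documents do not give, 1:1 allocation and a test that the plan does not name. At a 1-point shift the increase is modest, and a shift could run the other way.

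Masking the pathologist also does not mask the surgeon, so it reduces the exposure without removing it. None of this answers the core: the plan states no protection for its primary reading, and stating one is cheap.

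**Conclusion.** The point holds as a gap in specification. The trial is open-label, ypTNM 0-I and TRG are read from the surgical specimen, and nothing specifies that the reader is masked to arm. The only independent assessment covers imaging progression for a secondary endpoint, and it is not described as blinded.

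How much this matters depends on a reading shift that nobody can estimate from the documents. Under the assumptions stated, about one patient moved in the experimental arm matters little, while three to six would multiply the false-positive rate by roughly 2.6 to 4.3 one-sided (13.1/5.0 and 21.6/5.0). This is no finding that bias will occur and no criticism of any reader. It is a cheap improvement to the primary comparison. It has to be in place before specimens are sampled and read, because sampling effort cannot be restored afterwards.

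**What to change.** Add to sections 2.3 and 6.2:

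- The pathologists who assign ypTNM and TRG are masked to treatment arm.
- Specimens and pathology request forms carry a study number only, with no mention of allocation or of the tablet.
- The same specimen-sampling procedure applies in both arms.

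The existing pathologists can do this, so no extra reader is needed. The sample size, endpoint definitions and treatment are unchanged. The cost is the added text, a revised request form and minor specimen-handling work. Section 10 refers to participating centres, so the coding and the sampling procedure would have to be put in place at each one.

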been frequently cited in NCCN guidelines [9-11]. The mFOLFOX6 double-drug regimen (5-fluorouracil and leucovorin calcium in combination with oxaliplatin) is a highly potent chemotherapy regimen recommended by guidelines such as NCCN, EMSO, and CSCO for the first-line treatment of advanced colorectal cancer. However, it remains unclear whether the mFOLFOX6 double-drug regimen combined with Apatinib can enhance the treatment outcomes for patients with YWHAB high-expressing locally advanced rectal cancer. This requires further clinical research to confirm.

(2) Significance of the study

This study aims to conduct a prospective, open-label, double-arm, Phase II clinical trial. For patients with locally advanced rectal cancer, YWHAB immunohistochemical staining will be performed on colonoscopy biopsy specimens to identify patients with high YWHAB expression. These patients will then be randomly assigned to either the mFOLFOX6 treatment group or the mFOLFOX6 combined with Citrus Flavonoid Tablets (Aimalang) treatment group for neoadjuvant therapy. After completing 4-6 cycles of neoadjuvant chemotherapy, patients will undergo preoperative assessments by their attending physicians and have their tumors surgically removed by a specialized colorectal surgery team. Postoperatively, they will receive 6-8 cycles of adjuvant chemotherapy. The effectiveness and safety of the mFOLFOX6 combined with Citrus Flavonoid Tablets (Aimalang) regimen in neoadjuvant therapy for YWHAB high-expression locally advanced rectal cancer patients will be evaluated. This includes assessing the proportion of patients achieving tumor downstaging, the proportion of patients achieving pathological complete remission, the three-year disease-free survival rate, overall survival time, and tumor regression grade (TRG). The study is based on the team's previous basic research, animal experiments, and the clinical safety of Citrus Flavonoid Tablets (Aimalang), aiming to improve the efficacy of YWHAB high-expression locally advanced rectal cancer patients and benefit more patients.

2. Research design and purpose

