2.2 Research purpose

Main research objectives:

To evaluate the proportion of patients achieving tumor downstaging (ypTNM 0-I stage) in YWHAB high-expressing locally advanced rectal cancer treated with mFOLFOX6 combined with Citrus Flavonoid Tablets (Aimalang) as a neoadjuvant therapy, to provide evidence that Citrus Flavonoid Tablets (Aimalang) enhances the effectiveness of the mFOLFOX6 regimen in this patient population.

Secondary study objectives:

Efficacy evaluation: The proportion of pathological complete remission, 3-year disease-free survival (DFS), overall survival time (OS) and tumor regression grade TRG were evaluated in patients with YWHAB high expression locally advanced rectal cancer treated with mFOLFOX6 combined with citrus flavonoid tablets (Aimalang) as neoadjuvant therapy.

Safety evaluation: The treatment-related adverse reaction rate (grade 3 or above) of mFOLFOX6 combined with citrus flavonoid tablets (Aimalang) regimen for neoadjuvant treatment of YWHAB high expression local advanced rectal cancer patients was evaluated.

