8.3 Efficacy analysis and statistical methods

For the proportion of patients in each treatment group who achieved tumor downstaging (ypTNM 0-I stage), the proportion of participants with pathological complete remission, and the tumor regression grading (TRG), statistical analysis was conducted using mean values and standard deviations. For the three-year disease-free survival rate and overall survival time, Kaplan-Meier curves were plotted, and the 95% confidence interval for the median time was calculated using the Brookmeyer Crowley method. The Log-rank test was used to compare differences between groups, and the hazard ratios (HR) for each endpoint were

estimated using the Cox proportional hazards model, exploring the impact of factors other than treatment on these endpoints. Additionally, the number and percentage of cases that occurred at each endpoint, as well as the number and percentage of censored cases, were calculated and categorized by censoring reason.

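### Pathological complete remission is a named secondary endpoint, but the only definition printed for it is a clinical and imaging response scale that never refers to the surgical specimen

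*Combined protocol and SAP*

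**What the plan says.** The endpoint is named in four places, each time as a pathological outcome:

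- Section 1(2), Significance of the study: "the proportion of patients achieving pathological complete remission".
- Section 2.2, secondary objectives: "The proportion of pathological complete remission, 3-year disease-free survival (DFS), overall survival time (OS) and tumor regression grade TRG were evaluated".
- Section 6.1: "the secondary efficacy indicators were the proportion of patients with complete pathological remission".
- Section 8.3, efficacy analysis: "the proportion of participants with pathological complete remission".

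The only matching definition is item (1) of the secondary endpoints in section 2.3, repeated as item (2) in section 6.2. It opens with "The degree of pathological remission is defined as follows" and then gives four categories, CR, PR, SD and PD. CR is "All tumor target lesions have disappeared, no new lesions have appeared, and tumor markers are normal, lasting at least 4 weeks". PR is a fall of at least 30% in the summed maximum diameters, held for 4 weeks. PD is a rise of at least 20% or a new lesion. SD lies between them.

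Two other endpoints in section 2.3 bear on this one. The primary endpoint counts patients who "have their postoperative pathological stage of the surgical specimen classified as ypTNM 0-I stage". Secondary endpoint (4) is the tumour regression grade, where "TRG 0 means no residual tumor cells". Neither is linked to pathological complete remission.

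**The concern.** The heading of item (1) says pathological, but its content is clinical and radiological: visible lesions, their diameters, blood markers and a duration. The endpoint could therefore be reported in two ways under one name. An analyst who follows the printed text would count CR patients. An analyst who follows the endpoint's name would count patients whose specimen shows no tumour. Both could claim to follow the protocol, and the results could differ. Only the second count answers the secondary objective in section 2.2. In an open-label trial, leaving this choice until the results are known is best avoided.

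**Working it through.** The documents give no expected rate, sample size or power for this endpoint, so there is no figure to reproduce. The check is a comparison of the texts.

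**1. Is there a specimen-based definition elsewhere?** In the supplied text, no. Sections 1(2), 2.2, 6.1 and 8.3 use the name only. Sections 2.3(1) and 6.2(2) give the scale. No category of the scale mentions the specimen, residual cells, or a ypT or ypN category. No sentence equates the endpoint with CR, TRG 0 or ypTNM stage 0.

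**2. Can CR and the specimen disagree?** Both directions follow from the criteria.

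- *Specimen clear, CR not met.* A patient at TRG 0 fails CR if a tumour marker is abnormal, if a lesion is still visible on imaging, or if the 4-week duration was not shown.
- *CR met, specimen not clear.* A patient with no visible lesion, no new lesion and normal markers for 4 weeks meets CR whatever the pathologist finds, including TRG 1 to 3 or ypTNM stage II-III. At stage II-III the patient would count as a pathological complete remission while failing the primary endpoint. This case requires CR to be read before resection.

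**3. When is CR read?** The scale names no time, and neither reading works.

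- *After resection*, surgery has removed the target lesion, so its disappearance no longer reflects neoadjuvant treatment.
- *Before resection*, the imaging schedule does not support the 4-week condition. Section 5.2 places imaging after 6 and 12 cycles, while section 4.1 places surgery after 4-6 cycles. No confirmatory scan 4 weeks later is listed. Tumour markers are better covered, since section 5.2 lists them before each administration and section 5.3 at the end of treatment.

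**4. How far could the proportion move?** The discordance rate is unknown, so this shows sensitivity only. Section 8.5 gives 236 without saying whether it is a total, and no allocation ratio is stated. The formula is net discordant patients in one arm divided by the patients in that arm. The counts 2, 5 and 10 are assumed, and discordance in opposite directions cancels.

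| Net discordant patients in one arm | 236 total, equal split (236/2 = 118 per arm) | 236 per arm |
|---|---|---|
| 1 | 1/118 = 0.85 points | 1/236 = 0.42 points |
| 2 | 2/118 = 1.7 points | 2/236 = 0.8 points |
| 5 | 5/118 = 4.2 points | 5/236 = 2.1 points |
| 10 | 10/118 = 8.5 points | 10/236 = 4.2 points |

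**The case against.** The strongest reply is that pathological complete remission has a settled meaning, that ypTNM stage and TRG are endpoints in any case, and that the heading may be a translation slip. On that view nobody would count a ypTNM II-III patient as a complete remission, and nothing shows that the trial intends to. This limits the harm: the discordance is a logical consequence with no documented rate, and the stage II-III example depends on CR being both the rule and read before surgery. It does not remove the defect. A slip in a heading does not explain a full diameter scale printed twice, and the same section shows that its authors wrote a specimen rule where they wanted one.

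Four narrower objections deserve an answer.

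- *The appendices are not in the supplied text.* True, so the finding covers the supplied text only. Appendix 1 is cited for staging at eligibility, not for this endpoint.
- *TRG is not expressly tied to the specimen.* This stands in part. Sections 2.3(4) and 6.2(5) speak of residual tumour cells without naming the material, and the visit lists in sections 5.1 to 5.3 contain no reading of the resected specimen. The revised wording should name it.
- *Removing the scale removes the only printed numerical threshold for progression.* Section 6.2(3) already takes progression for DFS from RECIST 1.1, so DFS loses nothing. Section 4.1 also mentions progression, but does not refer to this scale.
- *The percentage-point figures apply to any binary endpoint, and the per-arm reading of 236 is unlikely.* Fair. They show sensitivity and do not estimate an error.

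**Conclusion.** The concern holds. The endpoint name and the only rule printed for it do not match, and applying the rule as written can misclassify patients against the specimen in either direction. The text mismatch is certain within the supplied document. The number of patients affected cannot be estimated from it, and the 0.85 points per discordant patient rests on 236 being a total split equally. The consequence is limited to ambiguous reporting of one secondary proportion. This should be corrected, but it does not threaten the trial's main conclusion.

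**What to change.** In sections 2.3(1) and 6.2(2), replace the CR/PR/SD/PD text with a definition read on the surgical specimen. One form that uses existing endpoints is no residual tumour cells in the primary tumour (TRG 0) and none in the examined lymph nodes, with its relation to ypTNM stage 0 stated. Say explicitly that TRG is read on the resected specimen.

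Report the proportion in the ITT set, which section 8.1 already makes the main set for efficacy. Count patients without a specimen as not achieving the endpoint. This matches the denominator rule in section 6.2, which is worded only for the primary endpoint and so needs extending. Leave the RECIST 1.1 reference for DFS in section 6.2(3) unchanged.

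The cost is wording in those two items. Sections 2.2, 6.1 and 8.3 already use the right name, and TRG and ypTNM stage are already endpoints. If the sponsor wants to keep the scale as a separately named clinical response, that costs more: its assessment time must be stated and reconciled with the imaging schedule in section 5.2, and imaging may have to be added.
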